To assess the difference in non-sedentary daytime physical activity between sacubitril/valsartan vs. enalapril treated patients during the treatment period (weeks 0 to 12).	
activity is defined as ≥ 178.5 activity counts per minute; light physical activity is defined as $178.5 - 565.5$ counts per minute; moderate-to-vigorous activity is defined as > 565.5 counts per minute. The average number of minutes per day spent in the different non-sedentary physical activity categories (light and moderate-to-vigorous) will be calculated over 14 day epochs.
 
Units of measure: descriptive statistics for quantitative data.
 
Time frame: baseline¹ epoch (i.e. week -2 to week 0), week 2 to week 4, week 6 to week 8, week 10 to week 12.
	
Title: Total weekly time spent in non-sedentary daytime physical activity.
 
Title: Total weekly time spent in light non-sedentary daytime physical activity.
 
Title: Total weekly time spent in moderate-to-vigorous non-sedentary daytime physical activity
 
Description: Non-sedentary physical activity is defined as ≥ 178.5 activity counts per minute; light physical activity is defined as $178.5 - 565.5$ counts per minute; moderate-to-vigorous activity is defined as > 565.5 counts per minute. The total time spent in non-sedentary physical activity and the time spent in light and moderate-to-vigorous physical activity will be calculated for each patient in weekly intervals and the temporal course for each patient will be assessed.
 
Units of measure: descriptive statistics for quantitative data.
 
Time frame: week 0 to week 12 in weekly epochs

To assess changes from baseline ¹ on M6min (an actigraphy-based measure of the peak six minutes of daytime physical activity) in sacubitril/valsartan vs. enalapril treated patients after week 4; week 8 and week 12.	
Title: Change from baseline¹ in M6min.
 
Title: Proportion of patients with increased M6min compared to baseline¹ at week 4, week 8 and week 12.
 
Description: M6min is a parameter derived by validated algorithms of the software that will be used to pre-process actigraphy data. The
	
Section 9.5

Objective	Endpoint	Analysis

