Note: according to the sacubitril/valsartan SmPC and the investigator's medical judgement, patients suffering from moderate hepatic impairment, moderate renal impairment or patients with SBP ≥100 to 110 mmHg should be initiated at dose level 1.

Two weeks (Visit 3) after randomization, up-titration is performed to the next higher level, provided good tolerability of the starting dose level; this means that patients, who started on dose level 2 or 2a will receive the target dose of study medication (level 3) at this point. Patients, who started study medication at dose level 1, will have a final up-titration after additional 2 weeks, i.e. at Visit 4. Therefore, after Visit 4 all patients will be receiving the target dose (level 3), unless safety issues prevent up-titration, or down-titration becomes necessary (see [Section 5.5.4](#)). See the following [Table 5-2](#) for an overview of up-titration scheme of study medication according to pre-study ACEI/ARB total daily dose.

Table 5-2 Study drug titration according to previous ACEI/ARB dose

Enalapril total daily dose before Visit 1 (week -2) (or equivalent dose of other ACEI/ARB, see Table 3-1)	Study drug dose level after randomization at Visit 2 (week 0)	Up-titration at Visit 3 (week 2)	Up-titration at Visit 4 (week 4)
< 5.0 mg/day	Dose level 1	Dose level 2	Dose level 3
5.0 mg to ≤ 10 mg/day	Dose level 2	Dose level 3	
>10 mg/day	Dose level 2a	Dose level 3	

Note: according to the sacubitril/valsartan SmPC and the investigator's medical judgement, patients suffering from moderate hepatic impairment, moderate renal impairment or patients with SBP ≥100 to 110 mmHg should be initiated at dose level 1.

All kits of study treatment assigned by the IRT will be recorded/databased in the IRT.

Patients will be instructed to take the study medication twice daily – once in the morning and once in the evening. The morning study drug dose should occur around 08.00 (8 am), the evening dose at approximately 19.00 (7 pm). The study medication should be taken with a glass of water with or without food. If the patient misses taking any study dose, he/she should take it as soon as possible, unless it is almost time for the following scheduled dose. In this case, the patient should be instructed to skip the missed dose and return to his/her regular study drug intake schedule.

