2 STUDY OBJECTIVES

[figure not shown]
Primary objectives

- To elucidate the change in physical activity as assessed by the distance walked in meters during the 6-minute walking test between baseline and 12 weeks of study drug treatment in sacubitril/valsartan vs. enalapril patients.
- To assess changes in daily non-sedentary daytime activity between baseline and after 12 weeks of treatment in sacubitril/valsartan vs. enalapril treated patients.

Secondary objectives

- To compare the proportion of patients with improved performance ($\geq 30m$) in the 6-minute walking test at week 12 between sacubitril/valsartan vs. enalapril treated patients.
- To demonstrate that sacubitril/valsartan is superior in improving exercise capacity as assessed by the six-minute walk test (6MWT) at week 12 in a subset of patients with baseline six-minute walk distance equal to or less than 300 meters
- To demonstrate that sacubitril/valsartan is superior in improving exercise capacity as assessed by the six-minute walk test (6MWT) at week 12 in the patients with baseline six-minute walk distance between 100-450 meters.
- To assess changes from baseline (week 0) in exercise capacity assessed by means of the 6-minute walking test at weeks 4, 8 and 12

- To compare the effects of sacubitril/valsartan vs. enalapril on patients' symptom progression by means of the Patient Global Assessment (PGA) questionnaire at week 4, week 8 and week 12.
- To assess dynamics of changes from baseline in daily non-sedentary daytime physical activity in sacubitril/valsartan vs. enalapril treated patients in weekly and two-weekly intervals.
- To assess changes from baseline in mean daily non-sedentary daytime physical activity classified by its intensity for sacubitril/valsartan vs. enalapril treated patients after week 4, week 8 and week12.
- To assess the difference in non-sedentary daytime physical activity between sacubitril/valsartan vs. enalapril treated patients during the treatment period (weeks 0 to 12).
- To assess changes from baseline on M6min (an actigraphy-based measure of the peak six minutes of daytime physical activity) in sacubitril/valsartan vs. enalapril treated patients after week 4; week 8 and week 12.

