Proportion of patients with improved symptoms of HF as assessed by PGA, number and proportion will be tabulated at week 4, week 8 and week 12. The comparison of patient groups will be presented and analyzed using a chi-square test or Fisher's exact test, where applicable.

Change from baseline in mean daily non-sedentary daytime activity in weekly and two-weekly intervals will be summarised. The comparison of patient groups will be analyzed using a two sample (independent group) t-test or a non-parametric Mann–Whitney–Wilcoxon (Wilcoxon rank sum) test, where applicable.

Proportion of patients at weekly and two-weekly intervals who show increased levels ($\geq 10\%$ increase) of mean daily non-sedentary daytime physical activity compared to baseline will be tabulated. The comparison of patient groups will be presented and analyzed using a chi-square test or Fisher's exact test, where applicable.

Change from baseline in mean daily light and moderate-to-vigorous non-sedentary daytime physical activity between baseline and different time points under treatment (weekly or two-weekly from week 0 to week 12) will be summarised. The comparison of patient groups will be analyzed using a two sample (independent group) t-test or a non-parametric Mann–Whitney–Wilcoxon (Wilcoxon rank sum) test, where applicable.

Total weekly time spent in non-sedentary daytime physical activity will be summarised by week, from week 0 to week 12. The comparison of patient groups will be analyzed using a two sample (independent group) t-test or a non-parametric Mann–Whitney–Wilcoxon (Wilcoxon rank sum) test, where applicable.

[figure not shown]
Total weekly time spent in light non-sedentary daytime physical activity will be summarised by week, from week 0 to week 12. The comparison of patient groups will be analyzed using a

[figure not shown]
two sample (independent group) t-test or a non-parametric Mann–Whitney–Wilcoxon (Wilcoxon rank sum) test, where applicable.

Total weekly time spent in moderate-to-vigorous non-sedentary daytime physical activity will be summarised by week, from week 0 to week 12. The comparison of patient groups will be analyzed using a two sample (independent group) t-test or a non-parametric Mann–Whitney–Wilcoxon (Wilcoxon rank sum) test, where applicable.

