Table 14.2-10 Improved performance (≥ 30 m) in 6MWT for patients with baseline 6MWT between 100-450 meters: logistic regression model.
FAS population/FAS population subset patients without AE/SAE
Statistical (logistic model) by treatment group

Table 14.2-11 6-minute walking test: absolute and change between baseline at week 4, week 8 and week 12 by treatment group.
FAS population/FAS population subset patients without AE/SAE
Descriptive statistics and statistical analysis by treatment group

Table 14.2-12 Increased levels ($\geq 10\%$ increase) of non-sedentary daytime physical activity: proportion of patients at the end of study by treatment group.
FAS population
Descriptive statistics

Table 14.2-13 Increased levels ($\geq 10\%$ increase) of non-sedentary daytime physical activity: logistic regression model.
FAS population
Statistical (logistic model) by treatment group

Table 14.2-14 PGA score at week 4, week 8 and week 12 by treatment group.
FAS population
Descriptive statistics and statistical analysis by treatment group

Table 14.2-15 Patients who improved symptoms of HF as assessed by PGA: proportion of patients at week 4, week 8 and week 12 by treatment group.
FAS population
Descriptive statistics and statistical analysis by treatment group

Table 14.2-16 Mean daily non-sedentary daytime activity: absolute and change in weekly and two-weekly intervals by treatment group.
FAS population
Descriptive statistics and statistical analysis by treatment group

Table 14.2-17 Mean daily non-sedentary daytime activity: Proportion of patients at weekly and two-weekly intervals who show increased levels ($\geq 10\%$ increase) by treatment group.
FAS population
Descriptive statistics and statistical analysis by treatment group

Table 14.2-18 Mean daily light and moderate-to-vigorous non-sedentary daytime physical activity: absolute and change by week and treatment group.
FAS population

[figure not shown]
Table 14.2-19	Descriptive statistics and statistical analysis by treatment group Total weekly time spent in non-sedentary daytime physical activity: absolute and change by week and treatment group.
Table 14.2-20	FAS population Descriptive statistics and statistical analysis by treatment group Total weekly time spent in light non-sedentary daytime physical activity: absolute and change by week and treatment group.

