Table 14.2-21	FAS population Descriptive statistics and statistical analysis by treatment group Total weekly time spent in moderate-to-vigorous non-sedentary daytime physical activity: absolute and change by week and treatment group.
Table 14.2-22	FAS population Descriptive statistics and statistical analysis by treatment group M6min: absolute and change between baseline at week 4, week 8 and week 12 by treatment group.
Table 14.2-23	FAS population Descriptive statistics and statistical analysis by treatment group Increase in M6min: proportion of patients at week 4, week 8 and week 12 by treatment group.
Table 14.2-27	 Interdaily Stability (IS): absolute and change between baseline at two-week intervals by treatment group.
Table 14.2-28	FAS population Descriptive statistics Intradaily Variability (IV): absolute and change between baseline at two-week intervals by treatment group.

Table 14.2-29 L5 average: absolute and change between baseline at two-week intervals by treatment group.
FAS population
Descriptive statistics

Table 14.2-30 M10 average: absolute and change between baseline at two-week intervals by treatment group.
FAS population
Descriptive statistics

Table 14.2-31 Relative amplitude: absolute and change between baseline at two-week intervals by treatment group.
FAS population
Descriptive statistics

Table 14.2-33 Mean daily sedentary daytime physical activity: Parameters (Δ , c, k, t0) and standard error from non-linear least square regression by treatment group.
Logistic function
FAS population
Descriptive statistics and statistical analysis (Δ)

Table 14.2-34 Mean daily light and moderate-to-vigorous non-sedentary daytime physical activity: Parameters (Δ , c, k, t0) and standard error from non-linear least square regression by treatment group. Logistic function
FAS population
Descriptive statistics and statistical analysis (Δ)

Table 14.2-35 M6min: Parameters (Δ , c, k, t0) and standard error from non-linear least square regression by treatment group. Logistic function
FAS population
Descriptive statistics and statistical analysis (Δ)

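### The visible SAP specifies no overall weeks 0–12 treatment contrast for the secondary objective on activity during the treatment period

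*SAP*

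**What the plan says.** SAP section 2 lists the objective: "To assess the difference in non-sedentary daytime physical activity between sacubitril/valsartan vs. enalapril treated patients during the treatment period (weeks 0 to 12". Protocol Table 2-1 gives it three endpoints: total weekly time in all non-sedentary activity, in light activity, and in moderate-to-vigorous activity. Their timing is "Time frame: week 0 to week 12 in weekly epochs". The description adds that the times "will be calculated for each patient in weekly intervals and the temporal course for each patient will be assessed".

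SAP 6.3.6 handles the first variable as "Total weekly time spent in non-sedentary daytime physical activity will be summarised by week, from week 0 to week 12", followed by "The comparison of patient groups will be analyzed using a two sample (independent group) t-test or a non-parametric Mann–Whitney–Wilcoxon (Wilcoxon rank sum) test, where applicable". The other two variables get the same treatment. The planned output, Table 14.2-19, is "Total weekly time spent in non-sedentary daytime physical activity: absolute and change by week and treatment group"; Tables 14.2-20 and 14.2-21 repeat that layout for light and moderate-to-vigorous time.

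Tables 14.2-33 to 14.2-35 list fitted time-course models giving curve parameters and "standard error from non-linear least square regression by treatment group. Logistic function", with a statistical analysis of a parameter Δ. They cover sedentary activity, light and moderate-to-vigorous activity, and M6min.

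Protocol 9.5.1 makes all secondary tests exploratory. SAP 6.4 sets 5% two-sided tests with no multiplicity adjustment.

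**The concern.** The objective is about a period, and the visible analysis is about weeks. A reader of the study report who wants to know how the arms differed in activity over the 12 weeks would find a row for each week and no row for the period.

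The weekly view already belongs to another objective. SAP section 2 separately lists the dynamics of change in weekly and two-weekly intervals, and 6.3.6 tests those as well. With complete recording, total weekly minutes are seven times mean daily minutes. So the period objective, as implemented, largely repeats the dynamics objective and leaves out the one result it could add.

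Nor does one week obviously stand in for the period. Protocol 5.5.4 states "Two weeks (Visit 3) after randomization, up-titration is performed to the next higher level", and patients who start at the lowest level are scheduled for a further step at Visit 4. The first four weeks therefore mix dose levels differently from the later ones.

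The weekly tests also carry no covariates. The table titles mention change as well as absolute values, but subtracting baseline is not the baseline and NYHA adjustment used in the primary ANCOVA.

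At stake is how well a secondary objective is answered. The primary conclusions are not at stake.

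**Working it through.** **1. What each place provides**

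| Place | Unit of analysis | Whole-period difference? |
|---|---|---|
| SAP 2, objective | weeks 0 to 12 | asked for |
| Protocol Table 2-1, endpoints | weekly epochs, plus each patient's course | not defined |
| SAP 6.3.6, three variables | summary by week, two-sample test | none stated |
| Tables 14.2-19 to 14.2-21 | by week and arm | none named |
| Tables 14.2-33 to 14.2-35 | curve parameters, Δ analysed | Δ undefined in visible text and not linked to this objective |

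The visible text for this objective has no period mean or total, no area under the curve, no repeated-measures model and no averaged contrast. The protocol's promise to assess each patient's course has no analysis in 6.3.6.

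**2. The plan's own figure**

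The documents give no precision figure for this objective. The nearest is the activity co-primary in SAP 4.2: difference 20 min/day, SD 70, two-sided 5%, 90% power.

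n per arm = 2 × (1.960 + 1.282)² × 70² / 20² = 258 by the normal approximation. The exact t calculation gives 259, the stated figure. It is not in dispute and serves only as the scale below.

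**3. Precision of a period mean (illustration)**

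Assumptions not in the documents:

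- the SD of one week's mean daily minutes is 70;
- the correlation r between any two weeks is equal, at 0.5 to 0.8;
- there are 259 patients per arm, no missing weeks and no covariate adjustment.

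Variance ratio of a 12-week mean to one week = (1 + 11r)/12. The SD of the mean is 70 × √ratio. The CI half-width is 1.96 × SD × √(2/259), where √(2/259) = 0.0879. For one week the half-width is 1.96 × 70 × 0.0879 = 12.1 min/day, and power at 20 min/day is 90.2%.

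| r | Variance ratio | SD of mean | Half-width | Power, constant 20 min/day |
|---|---|---|---|---|
| 0.5 | 0.542 | 51.5 | 8.9 | 99.3% |
| 0.7 | 0.725 | 59.6 | 10.3 | 96.8% |
| 0.8 | 0.817 | 63.3 | 10.9 | 94.9% |

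**4. The downside, on the same scale**

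Suppose the effect is zero in weeks 1–4 and 20 min/day in weeks 5–12. The period average is 20 × 8/12 = 13.3 min/day. Power is Φ(13.3/(SD × 0.0879) − 1.96), which gives 84%, 72% and 67% for r = 0.5, 0.7 and 0.8. A single late week has 90.2%. Averaging therefore gains precision but can lose power when the effect builds late.

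**5. Chance of at least one nominally significant week**

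Take 12 weekly tests of one variable at 5% with no true effect. By simulation with exchangeable correlation 0.5, 0.7 and 0.8, the chance is 32.0%, 23.3% and 18.5%. With AR(1) correlation at the same values it is 40.9%, 34.6% and 29.2%. If the weeks were independent it would be 1 − 0.95¹² = 46.0%. One period contrast stays at 5%.

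**The case against.** The strongest reply is that the SAP does what the protocol defined. Table 2-1 sets weekly epochs for this objective, and Protocol 3.2 says the continuous recording will be integrated in two-weekly bins, or weekly for certain endpoints. It promises no period contrast. This stands: the weekly displays are legitimate, and differences within weeks 0 to 12 are assessed.

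Four stronger readings are tempting, and the documents do not support them.

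- **That the trial never estimates this difference, or that no statistic combines the weeks.** Tables 14.2-33 to 14.2-35 list time-course fits with Δ analysed, and what Δ measures is not stated. Visible numbering skips SAP 3.3 and some tables (14.2-24 to 14.2-26 and 14.2-32), and Protocol 9.6 is redacted. Absence from the full plan cannot be proved.
- **That the report will hold 36 weekly p-values (12 weeks × 3 variables).** Repeating the test each week is the natural reading of 6.3.6 and the tables, but it is not stated. Total time is also the sum of the other two, so the three sets would not be separate evidence.
- **That error control fails.** Secondary tests are declared exploratory, with no multiple testing strategy. The probabilities above describe how easily one week may be picked out. They are not a breach of a stated error rate.
- **That every week is a different dose mix.** By the titration plan, up-titration is complete at Visit 4 for patients who tolerate it. About 8 of the 12 weeks are then past scheduled titration, and a period average mixes more dose levels than any one week does.

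Exploratory status answers the multiplicity argument. It does not supply the overall estimate.

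**Conclusion.** The point holds in a limited form. For the objective on activity during weeks 0 to 12, the visible SAP plans by-week summaries and two-sample tests without adjustment for baseline or NYHA class, and it names no overall treatment contrast. No visible text ties the Δ analyses to this objective. The weekly results are valid as far as they go, and the activity co-primary (weeks 10–12, ANCOVA) is untouched.

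The sizes are illustrative. A variance ratio of 0.54 to 0.82 and a 32% to 19% chance of at least one nominally significant week rest on assumed exchangeable correlations of 0.5 to 0.8. The half-widths and powers also assume a weekly SD of 70 min/day, and the power gain assumes a constant effect. The case for the change does not depend on these figures: the objective asks for a period difference, and the data to estimate it are already collected. It is a worthwhile, inexpensive improvement. Leaving it out would not undermine the trial's main findings.

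**What to change.** In SAP 6.3.6, for each of total, light and moderate-to-vigorous weekly time, add one between-arm difference with 95% CI averaged over weeks 1–12. Take it from a repeated-measures model on the weekly values with treatment, week, treatment-by-week, baseline weekly minutes and NYHA class (II vs. III/IV). State the baseline window; Table 2-1 already uses the last 7 days before randomisation for weekly comparisons. The model uses the available weeks of patients who drop out, under a missing-at-random assumption that should be written down, because SAP 6.6 addresses end-of-study values and not missing weeks. Keep the weekly results as supportive displays. Define Δ for Tables 14.2-33 to 14.2-35 and say which objective it serves.

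The cost is a paragraph of SAP text, three table rows and the programming, with no new data. It should be settled before database closure, when the SAP is to be final. The price in interpretation is that titration weeks are averaged in. That dilutes an effect that builds late, but it matches the stated objective, and the weekly displays would show such a pattern.

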6.3.7 Sensitivity analyses

6-minute walking test:

For the main analysis the patients who have an AE/SAE (non-HF related) during/around the 6-minute walking test which directly is causally linked to the 6-minute walking test performance will be removed. A sensitivity analysis will be performed including all patients for each population.

Main analysis for 6-minute walking test primary variable:

FAS population subset patients without AE/SAE (non-HF related) during/around the test

Sensitivity analyses for 6-minute walking test primary variable:

FAS population

PP population

PP population subset patients without AE/SAE (non-HF related) during/around the test

Mean daily non-sedentary daytime activity:

In addition to the primary analysis, the primary efficacy variables will also be analyzed using the same analysis model in the PP population as supportive. Furthermore, the analysis of the

primary variable (mean daily non-sedentary daytime activity) will be repeated in the FAS population without MI of missing values.

Besides, the last-observation-carried-forward principle (LOCF) imputation method will be performed as a sensitivity analysis (Section 6.6).

Main analysis for mean daily non-sedentary daytime activity primary variable:

FAS population with MI

Sensitivity analyses for mean daily non-sedentary daytime activity primary variable:

PP population with MI

PP population with LOCF

PP population without MI

FAS population without MI/LOCF

FAS population with LOCF

